2.2 Secondary objectives

To compare the efficacy of naloxegol (with placebo) in critically ill adults initiated on scheduled IV opioids on each of the following outcomes:

During the period from time of scheduled opioid therapy initiation (IV fentanyl equivalent dose \geq 100 mcg/day) until ICU discharge, death or 10 days of study drug administration (whatever comes first):

(Note: there are up to three days to enroll and randomize subject after the initiation of scheduled opioid therapy).

- a. Incidence of lower GI tract paralysis (\geq 3 days without a SBM)
- b. Time to first SBM (in hours)
- c. Days without a SBM
- d. Average daily opioid requirement [in IV fentanyl equivalents (mcg)].

Note:

1. For the purposes of inclusion in the study, only opioids administered by the IV route will be considered but to calculate the daily opioid requirement all opioids administered (regardless of route) will be considered. All enteral/oral opioids will be reduced by 50% when converting to the IV fentanyl equivalent.
2. Administration of opioids will be mandated by the ICU team (as per routine clinical practice based on the ICU team evaluation of regular pain assessment scores) and will not be protocolized as part of the study.
3. While IV fentanyl is the most common IV opioid used in the medical ICU at Tufts MC, other opioids (e.g. IV and oral hydromorphone, oral oxycodone) are used at times. Choice of opioid during routine patient care is currently not protocolized in the ICUs at Tufts MC and will not be protocolized as a part of this study. The choice and amount of opioid administered each day will be collected as part of the study.

During the period from time of study enrollment (i.e., randomization) to ICU discharge, death or 10 days of study drug administration (whatever comes first):

- e. Time to first SBM
- f. Daily characterization of each SBM for size (small, medium or large)
- g. Daily characterization of each SBM for consistency (using the Bliss Stool Scale)
- h. Daily characterization of use of the study laxative guidelines.
- i. Daily volume of enteral nutrition administered.
- j. % of daily enteral nutrition goal met.
- k. Daily fluid balance (i.e., 24 hr ins and outs)
- l. Daily maximal pain scale score (using nurse-administered 10 point rating scale)

Drug Substance: Movantik
 Study Number: ESR-15-11000
 Tufts IRB #12043
 Version: Protocol version #19
 Date: September 10, 2018

- m. Daily Sedation Assessment Scale (SAS) score
 - a. Average

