4. SUBJECT SELECTION CRITERIA

The investigators will maintain a screening log for the duration of the study.

Each patient will meet all of the inclusion criteria and none of the exclusion criteria. A study screening sheet will be completed by a member of the investigative staff and confirmed by a second member of the investigation staff before randomization will occur.

All patients consecutively admitted to the medical ICU service who are admitted to the MICU, CCU, SICU or NCCU at Tufts Medical Center will be screened on a daily basis (through review of the ICU admission note, available laboratory data, the medication administration record, and the patient flowsheet by one of the study investigators who will determine if the patient meets all inclusion and exclusion criteria for participation in the study).

When the patient is found to meet all inclusion and no exclusion criteria, and Drs. [name], [name] or [name] have reviewed and signed the screening form, and the patient's primary ICU attending has approved their enrollment, the subject/legally authorized representative will be approached (either in person or by phone (ie. invited to come to Tufts MC to discuss the study) during the periods of 7am to 7pm.

4. 1. Inclusion criteria

- a. Admitted to the medical ICU service.
- b. Age \geq 18 years.
- c. Expected by the medical ICU attending physician to require admission to the MICU service for \geq 48 hours.
- d. Intravenous opioid administration in the prior 24 hours of \geq 100 mcg fentanyl equivalents (including both scheduled and "as needed" therapy).

Drug Substance: Movantik
Study Number: ESR-15-11000
Tufts IRB #12043
Version: Protocol version #19
Date: September 10, 2018

e. No objections from the MICU or attending physician for enrollment.

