Other: _____			Start date: ____ / ____ / ____	Time: ____ : ____	Rate: ____ /hr

18. Opioid Medications at randomization: (check all that apply)

Fentanyl:	 Yes	 No	Start date: ____ / ____ / ____	Dose in last 24 hours ____ mcg
Hydromorphone:	 Yes	 No	Start date: ____ / ____ / ____	Dose in last 24 hours ____ mg
Morphine:	 Yes	 No	Start date: ____ / ____ / ____	Dose in last 24 hours ____ mg

Drug Substance: Movantik
Study Number: ESR-15-11000
Tufts IRB #12043
Version: Protocol version #19
Date: September 10, 2018

Oxycodone: Yes No Start date: ____/____/_____ Dose in last 24 hours ____ mg
Hydrocodone: Yes No Start date: ____/____/_____ Dose in last 24 hours ____ mg
Methadone: Yes No Start date: ____/____/_____ Dose in last 24 hours ____ mg
Other: _____ Start date: ____/____/_____ Dose in last 24 hours ____ mg

19. Reason for Opioid Initiation: (check all that apply)

- Analgesia for Mechanical Ventilation
- Postoperative Pain
- Cancer Pain
- Periprocedural Pain
- Wound Care

initials of investigational team member completing/verifying form _____ **date** _____

Baseline APACHE II Calculator

Pt Study ID: Pt Initials:

Please retain this worksheet at the site with the CRF.

Calculate APACHE II score using values from the 24 hour period prior to randomization.

Please circle appropriate range on form

A. Physiologic Variables Points

PHYSIOLOGIC VARIABLE	HIGH ABNORMAL RANGE					LOW ABNORMAL RANGE				PT SCORE
	4	3	2	1	0	1	2	3	4	
Temperature -core (°C)	≥ 41	39-40.9		38.5-38.9	36-38.4	34-35.9	32-33.9	30-31.9	≤ 29.9	
MAP (mmHg)	≥ 160	130-159	110-129		70-109		50-69		≤ 49	
Heart Rate	≥ 180	140-179	110-139		70-109		55-69	40-54	≤ 39	
Respiratory Rate (non-ventilated or ventilated)	≥ 50	35-49		25-34	12-24	10-11	6-9		≤ 5	
Oxygenation: [A-aDO ₂ = (FiO ₂ x 710) - (PCO ₂ x 1.25) - PO ₂]				FiO ₂ =	PCO ₂ =	PO ₂ =				

Drug Substance: Movantik
 Study Number: ESR-15-11000
 Tufts IRB #12043
 Version: Protocol version #19
 Date: September 10, 2018

a. If $\text{FiO}_2 \geq 0.5$ record A-aDO ₂	≥ 500	350-499	200-349		< 200					
b. If $\text{FiO}_2 < 0.5$ record only PaO ₂					PO ₂ > 70	PO ₂ 61-70		PO ₂ 55-60	PO ₂ < 55	
Arterial pH	> 7.7	7.6-7.69		7.5-7.59	7.33-7.49		7.25-7.32	7.15-7.24	< 7.15	
Serum Na (mEq/L)	≥ 180	160-179	155-159	150-154	130-149		120-129	111-119	≤ 110	
Serum K (mEq/L)	≥ 7	6-6.9		5.5-5.9	3.5-5.4	3-3.4	2.5-2.9		< 2.5	

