12.2 Methods of statistical analysis

[figure not shown]
Baseline characteristics of patients will be compared using standard univariate methods (chi-square test, t-test) to confirm the randomization was successful in achieving comparable groups. To test the primary outcome (incidence of lower GI tract paralysis), given that there may be censoring (i.e., subject may die or withdraw from study before developing lower GI tract paralysis), we will present Kaplan-Meier curves for the naloxegol and placebo groups for the time to first development of lower GI tract paralysis (≥ 3 days without a SBM after study randomization) during the ICU stay up to 10 days and compare the curves using a log-rank test. If all subjects complete the study (e.g., no deaths, no withdrawal or loss-to-follow-up for other reasons), then we will instead compare the proportion of patients that develop lower GI tract paralysis after study randomization during the ICU stay up to 10 days between the naloxegol and placebo groups using a chi-square test. The secondary outcome, time to first SBM will be estimated using a Kaplan Meier time to event analysis and compared between groups using a log-rank test. The secondary outcome of the number of ICU days without a SBM will be compared between the naloxegol and placebo groups using the Poisson regression for count data and adjusting for total number of days in the ICU (up to a maximum of 10) as an offset term in the Poisson model. The secondary outcome of the average daily opioid requirements will be compared between groups using either a student t-test or nonparametric Wilcoxon rank-sum test if the assumptions of the student t-test fail to be met. Length of mechanical ventilation and ICU stay will be reported as medians and interquartile ranges and will be compared using the Wilcoxon Rank Sum Test. For all statistical tests of hypotheses, a two-sided p-value of ≤ 0.05 will be considered as statistically significant. As this is a Phase II proof of concept study a p value of <0.10 may still be worth consideration for future study, however. All statistical analyses will be performed using SPSS 17.0. (SPSS, Chicago, IL) or other comparable commercially available statistical software.

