12.2.2 Determination of sample size

For the power analysis, the 4-day estimates of failure to defecate (i.e., failure to have a SBM) from the Kaplan-Meier plot presented in the Guardiola et. al. paper [4] was used as the estimate of lower GI tract paralysis. The figure below shows that the estimate of the percent of patients who failed to defecate (1 minus plotted proportion with defecation) by day 4 was 40% in the Prophylaxis group (i.e., the intervention group) vs. 90% in the non-prophylaxis (Treatment) group (i.e., the control group) (see yellow highlights in figure). We believe the 4-day estimate will be strongly related to the primary outcome of lower GI tract paralysis (≥ 3 days without a SBM).

90% (Placebo) vs. 40% (Prophylactic treatment), all subjects have complete follow-up, and the analysis is done using the log-rank test to compare survival curves. As sensitivity analysis, the table also shows the power of the study with this sample size under different scenarios. Because this is not the final definitive study to determine efficacy, a less stringent alpha of 0.10 may be justified for this Phase II proof-of-concept study which, if positive, would be followed by a confirmatory study [15]. While we expect most subjects to finish the study (based on the inclusion criteria), we have shown the impact on the power if approximately 20% of subjects do not finish the study. We have also varied the estimated proportion of patients failing to defecate by day 4 (i.e., not having a SBM) in the placebo group from 90% to 70% and in the prophylactic treated group from 40% to 50%.

Statistical Power of Log-Rank Test with n=18 subjects per group (36 total)

Complete study	ALPHA	Proportion Failing to Defecate at Day 4 (Placebo vs. Prophylactic Treated)				
		90% vs. 40%	90% vs. 50%	80% vs. 40%	80% vs. 50%	70% vs. 40%
100%	0.05	99.8%	98.4%	92.7%	76.0%	76.0%
	0.10	100.0%	99.4%	96.2%	84.9%	84.9%
80%	0.05	99.7%	97.6%	90.8%	72.5%	72.5%
	0.10	99.9%	99.0%	95.1%	82.2%	82.2%

For this Naloxogol randomized trial, we propose enrolling 36 subjects, 18 per group. The statistical power table below shows this sample size yields over 95% power using an alpha of 0.05 if the true day 4 estimated freedom of event (defecation) rates are

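### Average daily opioid dose is compared without the baseline dose already on the case report form, over a window that opens before randomisation; adjusting is a cheap gain of uncertain size

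*SAP*

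**What the plan says.** SAP 12.2, repeated word for word in Protocol 12.2, has the average daily opioid requirement "compared between groups using either a student t-test or nonparametric Wilcoxon rank-sum test if the assumptions of the student t-test fail to be met". It names no covariate, no log scale, no criterion for when the t-test assumptions fail, and no effect estimate or confidence interval for this outcome.

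Protocol 2.2 lists the outcome as secondary objective d, in IV fentanyl equivalents over all routes. It belongs to the group of outcomes measured "During the period from time of scheduled opioid therapy initiation", and a note adds that "there are up to three days to enroll and randomize subject after the initiation of scheduled opioid therapy".

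The baseline form (Appendix 11, item 18) is headed "Opioid Medications at randomization: (check all that apply)" and asks for "Dose in last 24 hours" for each opioid. Inclusion criterion d also uses a prior-24-hour dose: "Intravenous opioid administration in the prior 24 hours of" at least 100 mcg fentanyl equivalents. On sample size, SAP 12.2.2 says "we propose enrolling 36 subjects, 18 per group".

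**The concern.** Opioid dosing is not protocolised (Protocol 2.2, note 2). Entry has a floor of 100 mcg in 24 hours but no ceiling, and Protocol 1.1 mentions high-dose infusions. Doses are therefore likely to vary widely between patients and to be right-skewed. The dose just before randomisation is a natural predictor of the dose afterwards. An unadjusted comparison leaves all that between-patient variation in the error term, which matters with 18 per arm.

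The window is a second problem. Days before randomisation cannot be affected by study drug. Including them pulls the two arms together. It also puts the 24 hours that would serve as covariate inside the outcome.

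At stake is how much a null result on opioid requirement can tell the reader. A trial meant to inform the design of later ones (Protocol 1.2) would also gain from an adjusted ratio and its residual spread.

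**Working it through.** **Inputs from the documents.** 18 per arm; two-sided 0.05 (SAP 12.2); unadjusted t-test or Wilcoxon; baseline dose recorded; up to three days between opioid initiation and randomisation. The documents give no effect, SD, correlation or power for this outcome, so there is no planned figure to reproduce. Protocol 1.2 itself says that effect and variability are unclear.

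**Assumptions.** Lognormal doses; baseline and later log dose correlated at r; log SD 0.8 or 1.0; true ratio of geometric means 0.5; outcome measured only after randomisation; no zero doses.

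**Step 1: closed form.** Adjustment multiplies the residual SD by √(1 − r²). On the log scale:

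power ≈ Φ( |ln ratio| / [SD × √(1 − r²) × √(2/18)] − 1.96 ), where |ln 0.5| = 0.693 and √(2/18) = 0.333.

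- SD 0.8, unadjusted: 0.693/0.267 = 2.60; Φ(0.64) = 73.9%.
- SD 0.8, r 0.5: 0.693/(0.267 × 0.866) = 3.00; Φ(1.04) = 85.1%, gain 11.2 points.
- SD 0.8, r 0.7: 0.693/(0.267 × 0.714) = 3.64; Φ(1.68) = 95.4%, gain 21.5.
- SD 1.0, unadjusted 54.8%; gains 3.9 at r 0.3, 12.3 at r 0.5 and 28.2 at r 0.7.

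**Step 2: simulation of the planned procedure.** The SAP gives no rule for choosing the test. The simulation used Shapiro-Wilk p > 0.05 in both arms for the t-test, otherwise Wilcoxon, on untransformed dose. That rule is an assumption of this check.

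| Log SD | r | Planned rule | Log ANCOVA | Gain (points) |
|---|---|---|---|---|
| 0.8 | 0.3 | 69% | 75% | 6 |
| 0.8 | 0.5 | 69% | 82% | 13 |
| 0.8 | 0.7 | 69% | 94% | 25 |
| 1.0 | 0 | 49% | 51% | 2 |
| 1.0 | 0.3 | 48% | 54% | 6 |
| 1.0 | 0.5 | 49% | 63% | 14 |
| 1.0 | 0.7 | 49% | 79% | 30 |

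Repeat runs agreed to within a few points. The last cell ranged from 28 to 33. At r = 0 the log scale more than repays the lost degree of freedom.

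**Step 3: where the gain shrinks.** With log SD 0.6 the planned rule already has about 90% power; the gain is then 3 points at r 0.3 and at most about 10 even at r 0.8. For a 20% reduction at log SD 0.8 to 1.0, the gain is only a few points at r 0.3 to 0.5 and at most about 8 at r 0.7, with power no higher than about 20% by either method.

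**Step 4: type I error.** The planned rule gave 4.2 to 5.4%; ANCOVA gave 4.0 to 6.3% across runs.

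**Step 5: the window.** Suppose daily dose is constant apart from a halving at randomisation, with three days before it. With ten days after, the from-initiation ratio is (3 + 10 × 0.5)/13 = 0.62 instead of 0.50. With four days after, it is (3 + 4 × 0.5)/7 = 0.71. These are illustrations of dilution at the longest permitted delay.

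**Step 6: zeros.** The from-initiation average includes the qualifying dose, so it should not be zero. An average from randomisation onward can be, because qualifying doses may be given as needed. With 5% zeros (assumed), median 1,000 mcg, log SD 0.8, r 0.5 and a true halving, the planned rule has 58% power. Log ANCOVA has 33% after adding 1 mcg, 41% after adding 10 mcg and 59% after adding 100 mcg. Rank-based ANCOVA has 66%.

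**The case against.** The strongest reply is that a t-test or Wilcoxon test is conventional and, under randomisation, valid. This is one of about 20 secondary outcomes in a proof-of-concept trial that was not sized for it. Pain, sedation and withdrawal scores bear on the same question. All of that stands, and it limits this point to an efficiency improvement.

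The size of the gain is also open to challenge, because no document supplies r, SD or effect. That stands too: the table in the working is conditional and must be read so.

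A further objection is that log ANCOVA with an unspecified added constant could do worse than the plan. Step 6 confirms it. This rules out a careless form of adjustment, but not adjustment itself, since the rank-based version kept an advantage in that setting.

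Two stronger readings are tempting. A reader might infer that choosing the test after seeing the data inflates false positives; in simulation it did not. A reader might also infer that a chance imbalance in baseline dose would pass for a drug effect. Imbalance is likely at this size: with log SD 0.8 to 1.0, baseline geometric means differ more than 1.3-fold in about 33 to 43% of trials. But the 5% error rate of the unadjusted test already allows for it. What remains is lost precision, and a baseline comparison in SAP 12.2 with no stated consequence if the arms differ.

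**Conclusion.** The point holds as a low-cost improvement. The planned comparison is valid but leaves out a baseline dose that the trial already collects. At 18 per arm, with a true halving, log SD 0.8 to 1.0 and no zeros, adjustment is worth about 2 points at r = 0, 6 at 0.3, 12 to 14 at 0.5 and 24 to 30 at 0.7. A reader might take the upper figures as the expected benefit. The documents do not support that: the gain is small if r is low, if the effect is small, or if planned power is already high.

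The window finding needs no assumed SD or correlation. As written, secondary objective d averages in days before treatment, and that average can overlap the proposed covariate. The window and the adjustment should be settled together.

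**What to change.** 1. In Protocol 2.2 (objective d) and in section 12.2 of both documents, define the compared outcome as average daily opioid dose from randomisation onward. Report the from-initiation average descriptively.

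2. Replace the sentence in 12.2 with:

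> Average daily opioid dose after randomisation (IV fentanyl equivalents) will be compared by ANCOVA adjusting for the dose in the 24 hours before randomisation, converted to fentanyl equivalents in the same way. If no post-randomisation average is zero, the log scale is used and a ratio of geometric means with 95% CI is reported. If any is zero, rank-based ANCOVA on the same covariate is used and no constant is added. The unadjusted Wilcoxon test is a sensitivity analysis.

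The conversion clause is needed because item 18 lists each opioid separately.

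Cost: one degree of freedom, and a wording change to the objective as well as to the SAP. If zeros occur, the rank-based analysis gives no ratio of geometric means. No new data collection is needed.

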All patients will be evaluated by a member of the investigative team to determine if they have the mental capacity to provide consent for study participation. For the purposes of this study, a patient will be deemed to be cognitively intact if they have an ICDSC=0 (i.e. neither delirium nor subsyndromal delirium) and are not sedated. It is expected that the vast majority of patients will be not able to initially provide consent given their critical care illness and the use of scheduled opioids that have sedative properties. In addition, it is estimated that about two-thirds of the potential subjects will be mechanically ventilated and thus all be received sedative medications. Furthermore, close to 70% of patients of all patients admitted to the ICU have delirium or subsyndromal delirium, cognitive states that prevent obtaining consent from subjects. Drs. [name], [name], [name], [name], [name] and [name] will each be able to determine whether the subject is able to provide informed consent. As per the ICF, a legally recognized representative will be recognized in the following order: healthcare proxy (that is documented and verified) > spouse >adult child > parent of guardian > adult sibling.

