5.2.2 Procedures for randomization

Subjects meeting all inclusion criteria and no exclusion criteria will be randomized by a pharmacist in the Tufts Medical Center investigational drug pharmacy to one of two study groups (ie. naloxegol or placebo) on the first day. Randomization (in blocks of 4) will take place by means of a computer-generated random-number table and will be developed by a pharmacist in the Tufts Medical Center investigational drug pharmacy. This randomization schedule will assign each subject a study number, which will be used to identify treatment allocation (ie. naloxegol or placebo) and all study data that is collected during the study.

5.3 Procedures for handling subjects incorrectly enrolled, randomized or initiated on the investigational product.

Both the investigative team and the research pharmacists in the investigational drug pharmacy have extensive experience in conducting randomized, double-blind, medication-based trials in the ICUs at Tufts Medical Center. An investigational screening sheet is always completed and verified by a secondary member of the investigative team before a patient/family is approached for consent and before randomization occurs. Should the very unlikely situation occur that a patient is mistakenly enrolled in the study or consent is withdrawn by the patient (family member), a member of the investigative team will contact the study PI, the patient's primary physician and the investigation drug pharmacy regarding this issue. In all situations the Tufts Med Center IRB and AstraZeneca will be informed of this occurrence in a timely fashion.

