 Tufts operating room following emergency surgery	

Drug Substance: Movantik
Study Number: ESR-15-11000
Tufts IRB #12043
Version: Protocol version #19
Date: September 10, 2018

10. Prior ICU stay during this hospital admission: Yes No

If YES, specify unit: _____

11. Was a tracheotomy present on admission to ICU? Yes No

If YES, was it performed during this hospital admission? Yes No

12. Start date of mechanical ventilation: Date: ____/____/____ Time: ____:____ (24hr clock)

13. Admission APACHE III Diagnosis Code (Please see attached): _____

If "other" has been selected in any category, please specify: _____

14. APACHE II Score (Please see attached): Calculate APACHE II score using values from the 24 hour period prior to randomization.

APS: _____

Age Points: _____

Chronic Health Points: _____

Total APACHE II: _____

initials of investigational team member completing/verifying form _____ date _____

Drug Substance: Movantik
 Study Number: ESR-15-11000
 Tufts IRB #12043
 Version: Protocol version #19
 Date: September 10, 2018

Pt Number	Patient Initials	Date
____ / ____ / ____	____ - ____ - ____	

15. Baseline SOFA Score (Please see attached): Calculate SOFA score using values from the 24 hour period prior to randomization.

Total SOFA: ____

16. Last Spontaneous Bowel Movement (Per medical record review/family interview):

Date: ____ / ____ / ____

Time: ____ : ____ (24 hour clock)

17. Current infusions at randomization: (check all that apply)

Fentanyl:	 Yes	 No	Start date: ____ / ____ / ____	Time: ____ : ____	Rate: ____ mcg/hr
Hydromorphone:	 Yes	 No	Start date: ____ / ____ / ____	Time: ____ : ____	Rate: ____ mg/hr
Morphine:	 Yes	 No	Start date: ____ / ____ / ____	Time: ____ : ____	Rate: ____ mg/hr
Midazolam:	 Yes	 No	Start date: ____ / ____ / ____	Time: ____ : ____	Rate: ____ mg/hr
Lorazepam:	 Yes	 No	Start date: ____ / ____ / ____	Time: ____ : ____	Rate: ____ mg/hr
Propofol:	 Yes	 No	Start date: ____ / ____ / ____	Time: ____ : ____	Rate: ____ mcg/kg/min
Dexmedetomidine:	 Yes	 No	Start date: ____ / ____ / ____	Time: ____ : ____	Rate: ____ mcg/kg/hr

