12. STATISTICAL METHODS AND SAMPLE SIZE DETERMINATION

12.1 Description of analysis sets

All patients will be analyzed in the groups to which they were randomly assigned, according to the intention-to-treat principle.

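### Length of ventilation: if never-ventilated patients count as zero, the planned unstratified Wilcoxon test is valid but imprecise; define the variable and stratify by ventilation at randomisation

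*SAP*

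**What the plan says.** SAP 12.2 (repeated in Protocol 12.2): "Length of mechanical ventilation and ICU stay will be reported as medians and interquartile ranges and will be compared using the Wilcoxon" rank-sum test. It names no stratum, covariate or subset.

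SAP 12.1: "All patients will be analyzed in the groups to which they were randomly assigned, according to the intention-to-treat principle". No ventilated-only analysis set is defined.

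Protocol 4.1 does not make ventilation an inclusion criterion. Protocol 5.2.1, on capacity to consent, says "it is estimated that about two-thirds of the potential subjects will be mechanically ventilated". Protocol 5.2.2 says "Randomization (in blocks of 4) will take place by means of a computer-generated random-number table" and mentions no stratification.

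Protocol 2.2, objective q, names a different variable from the SAP: days free of ventilator support, counted from randomisation to ICU discharge, death or 10 days of study drug. SAP 12.2 speaks of length and gives no window. Neither place says how deaths or never-ventilated patients are scored.

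The data for stratifying are already collected. Table 1 has a row for requirement for ventilation that starts before randomisation, and Appendix 11 item 12 asks for the "Start date of mechanical ventilation".

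**The concern.** If about a third of patients enter with a length of zero, most of those zeros reflect the patient's state at entry and not treatment. An unstratified rank test ranks them together with the ventilated patients, so the rank sum becomes largely a count of who was ventilated at entry in each arm. Randomisation does not balance that count by design.

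This would cost precision in a trial of 36 patients. A pooled median and interquartile range would also mix two populations, which matters because Protocol 1.2 wants this study to describe endpoint variability for later trials.

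**Working it through.** **The plan's own power figure.** The documents give power only for the primary log-rank test and none for ventilation. For the 90% vs 40% column, exponential curves through day 4 give a hazard ratio of ln 0.9 / ln 0.4 = 0.115. Events over 10 days are 18 × [(1 − 0.9^2.5) + (1 − 0.4^2.5)] = 18 × (0.232 + 0.899) = 20.3. Then z = |ln 0.115| × √20.3 / 2 − 1.96 = 2.92, which is power 99.8%, as stated. It has no bearing on ventilation.

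**Inputs.** From the documents: 18 per arm, two-sided 0.05, two-thirds ventilated. Assumed: never-ventilated patients score zero; durations are log-normal with log-SD 0.8 (the median, 5 days, does not affect ranks); 10% of those not ventilated at entry are ventilated later; treatment does not change who is ventilated. The documents give no distribution or effect size for ventilation.

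**How much of the statistic is baseline status.** Take 24 of 36 ventilated and nobody ventilated later. The 12 zeros share mid-rank 6.5. The ventilated hold ranks 13 to 36, with mean 24.5. About the overall mean of 18.5:
- between groups: 24 × 6² + 12 × 12² = 864 + 1728 = 2592
- within the ventilated: 24 × (24² − 1) / 12 = 1150
- total: 3742

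The between-group share is 2592 / 3742 = 69%. Simulation with no treatment effect gives about 68%.

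**What a given split does with no treatment effect.** The rank-sum variance is [18 × 18 / (36 × 35)] × 3742 = 962, SD 31.0. Each ventilated patient above an arm's expected 12 moves its rank sum by 24.5 − 6.5 = 18.
- 12 vs 12: no shift. Conditional SD is √[12 × 12 / (24 × 23) × 1150] = 17.3, or 0.56 on the z scale. Rejection needs 1.96 / 0.56 = 3.5 SD, so it happens in under 0.1% of trials.
- 14 vs 10: z shifts by 36 / 31.0 = 1.16, with conditional SD 0.55. Rejection probability is P(N > (1.96 − 1.16) / 0.55) = 7%.
- 15 vs 10 (25 ventilated, 11 zeros): z shifts by 2.5 × 18 / 31.2 = 1.44, with conditional SD 0.58. Rejection probability is 19%.

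With 10% ventilated later, simulation gives 0.3%, 8% and 16%; the stratified test stays at about 5% throughout.

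**How often the arms differ.** With two independent binomials (18, 2/3), P(gap ≥ 4) = 0.215 and P(gap ≥ 5) = 0.110.

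**Power.** The comparator is van Elteren: sum over strata of (W − E) / (N + 1), with variance the sum of V / (N + 1)². It is simulated under the assumptions above.

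| Share ventilated | Duration ratio | Unstratified | Stratified |
|---|---|---|---|
| 2/3 | 1.0 (type I error) | 5% | 5% |
| 2/3 | 0.5 | 22% | 45% |
| 2/3 | 0.6 | 14% | 27% |
| 2/3 | 0.7 | 10% | 16% |
| 2/3 | 0.8 | 7% | 9% |
| 80% | 0.5 | 36% | 57% |
| 90% | 0.5 | 51% | 63% |

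Repeat runs agree within about three percentage points. With halving at a two-thirds share, log-SD 0.6 gives about 32% vs 67% and log-SD 1.0 gives 16% vs 32%.

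**The case against.** **The zero coding is not written.** A reader might infer that the plan scores never-ventilated patients as zero. SAP 12.1 fixes the groups in which patients are analysed, not the value given to a patient with no duration, and SAP 12.2 names no denominator. This stands, and it is why the conclusion is conditional. A ventilated-only reading is not expressly excluded. If it meant ever ventilated, it would select patients partly on events after randomisation and sit badly with 12.1.

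**The test is not wrong.** A reader might infer from the 14 vs 10 and 15 vs 10 splits that it produces too many false positives. It does not: averaged over the splits randomisation produces, type I error is about 5%. Any unadjusted test behaves this way when a prognostic factor is unbalanced by chance. Stratifying buys precision; it does not correct an error.

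**The loss is not always half.** It depends on a large assumed effect and on a two-thirds share that describes potential subjects in a consent section, not randomised patients. The table shows the gap narrowing as the share rises or the effect shrinks. Even in the base case the stratified test misses more than half of true halvings.

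**The protocol does not claim power here.** Protocol 1.2 leaves duration of ventilation to larger, adequately powered investigations. That limits the importance of the point, but it gives no reason to keep the less precise test when the stratifier is already recorded.

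**ICU stay.** The same SAP sentence covers ICU stay, and a reader might extend the point to it. Every patient has an ICU stay, so the block of zeros is absent, and no calculation here supports a change.

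**Conclusion.** The point holds as a free improvement to one secondary outcome of a pilot. The plan leaves open which ventilation variable is tested and how never-ventilated patients and deaths are scored. If never-ventilated patients enter as zero, the planned test is valid but inefficient, and roughly two-thirds of the variance of its statistic under no effect comes from the arm difference in number ventilated.

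In the base case (18 per arm, two-thirds ventilated, log-SD 0.8, duration halved), power is about half that of a stratified test. The advantage is about 21 points at an 80% share (57% − 36%), 12 points at 90% (63% − 51%), and negligible for a ratio of 0.8 at a two-thirds share. These sizes rest on the assumed distribution, the effect sizes and the zero coding. They apply to length of ventilation and not directly to days without it.

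**What to change.** In SAP 12.2 and Protocol 12.2:

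1. Choose one ventilation variable and its window, so that SAP 12.2 and objective 2.2q agree. The choice comes before the test, because the two can treat death in opposite directions: an early death shortens length of ventilation, but would normally count against days without it.
2. State how deaths and never-ventilated patients are scored in that variable.
3. Compare it in all randomised patients by a Wilcoxon test stratified by ventilation at randomisation (van Elteren). Take status from the Table 1 ventilation row together with the Appendix 11 start date; a start date alone does not show that the patient was still ventilated at randomisation.
4. Report the number ventilated at randomisation in each arm, and medians with interquartile ranges separately by that status.

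The stratifier is fixed at randomisation, so this respects SAP 12.1. The test for ICU stay can remain as it is. The cost is a few sentences, agreed before the treatment codes are opened, with no new data and no extra patients.
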